## **5 Study Objectives**

### **5.1 Primary Objective**

To assess the food effect on bioavailability ( $AUC_{0-\infty}$ ,  $AUC_{0-t}$  and  $C_{max}$ ) for the fixed dose combination Metformin 1000 mg/Gliclazide 30 mg MR, given as single dose in fed and fasted state to healthy volunteers.

### **5.2 Secondary objectives:**

- ✚ Additional Pharmacokinetic parameters will be determined:  $t_{1/2}$ ,  $t_{max}$ ,  $Vz/f$  and  $Cl/f$ .
- ✚ To assess and compare safety and tolerability of the fixed dose combination Metformin /Gliclazide administered in fast and fed state.

## **6 Investigational Plan**

### **6.1 Experimental design and study plan**

The IMP will be given in fast and fed state. A randomized, open label, single dose,  $2 \times 2$  cross design will be used with a 14-day washout period between 2 study stages. Treatment groups will be balanced, with the same number of subjects, who will be randomized to the dosing sequences (see table below).

Food's effect study			
Sequence	Period 1	Washout period	Period 2
1	Fast		Fed
2	Fed		Fast

All data from participant subjects should be analyzed and included in the statistical analysis, as long as they meet the established criteria.

## **6.2 Rationale for Study Design**

As per international clinical guidelines about Type 2 Diabetes management (Diabetes Care, 2014), Metformin, if there are no contraindications and if this is tolerated, is the drug of choice for Type 2 Diabetes. In the event Metformin monotherapy at the maximum tolerated dose does not maintain A1c target for more than 3 months, then it will be necessary to add a second oral agent from another pharmacological family, such sulphonylureas, thiazolidine, DPP4i or GLP-1-RA.

Gliclazide is a second generation sulphonylurea which offers a complementary mechanism of action for Metformin. On the other hand, there is wide experience about Metformin and Gliclazide association and it is particularly recommended by some clinical guidelines (Theobald, 2014) when Metformin monotherapy is not enough to achieve treatment objectives.

Therefore, a fixed dose combination has been developed as second line therapy, in cases when Metformin's monotherapy has not shown a satisfactory benefit/risk ratio. Therefore, this fixed dose combination for Metformin and Gliclazide is a generic for the existent concomitant administration of these two active ingredients which use is already generalized. Fixed dose combination has the potential advantage of making easier the therapy by reducing the number of individual dosage units to be taken by the patient. This simplifies therapy and may improve patient's compliance (Diabetes Care, 2014; Treatment Algorithm for Type 2 Diabetes, 2014.)

Prior to this proposed study, a study to assess bioequivalence between fixed dose and concomitant administration was performed, in addition to the lack of drug - drug interaction.

According to the international guidelines, studies to compare relative bioavailability in fasting and food conditions are necessary for combined modified release drugs, such as the combination proposed herein. Therefore, as part of the full clinical development for the fixed dose combination, food interaction should be studied. Study design adheres to the Mexican regulations as well as to the international guidelines for food assessment (Diabetes Care, 2014).

The purpose of this clinical study is to assess the food effect on bioavailability for the new fixed dose combination for Metformin 1000 mg/Gliclazide 30 mg MR.

In addition to the inclusion and exclusion criteria, potentially confounding factors to be controlled are: fast state and dosing immediately after food intake, as well as the type breakfast; morning schedule for treatment's dosing; volume and type of liquids to drug's intake; schedule, type and amount of food; physical activity restricted to minimum which does not modify heart rate; supine or seated positions up to reaching the stated time for  $t_{max}$ ; exclusion of caffeine and/or theophylline products; controlled access to the health services until reaching stated time for  $t_{max}$ . In addition, concomitant use of drugs is not allowed, unless prescribed drugs for adverse events, with the exception for paracetamol that can be given if required, as per the Principal Investigator's judgment

This study will be carried out in male and female healthy volunteers.

## **6.3 Study population screening**

Only those people who meet all inclusion criteria and no exclusion criteria will be recruited as study subjects. Before performing any study specific assessment which is not part of the subject's routine health care, the Principal Investigator will make sure that the subject has provided his/her written consent form according to the procedure described in section 9.2, Subject's information and informed consent form.

- Recruitment by invitation by means of an open announcement.
- Inclusion of 22 subjects in study as per protocol's criteria.
- Female and male (at least 40 % for each gender by group).

### **6.3.1 Inclusion criteria:**

Subject grants informed consent prior any study related activity will be performed.

1. Ethnicity: Mexicans (e.g., Caucasian, native people and Mestizo [mixed race])
2. Gender: Female and male (at least 40 % for each gender by study group).
3. Age between 18 and 55 years old, both including.
4. Weight between 55 and 95 kg.
5. Body mass index between 18 and 27 kg/m^2.
6. Non smokers or subjects who do not smoke more than 5 cigarettes or 1 pipe a day
7. Good physical and mental health based on the clinical history and physical examination.
8. All results from blood chemistry, hematology, and urinalysis should be within normal ranges or without clinically significant deviations as per Principal Investigator's judgment\*.
9. Hematology complete blood count [CBC]: hematocrit and hemoglobin must be above the lower limit; upper limit may range up to 15 %. Remaining results, including white blood cells may range  $\pm$  15 %, if subject is asymptomatic.
10. Liver Function Test, including direct and indirect bilirubin, glutamic oxaloacetic transaminase (aspartate aminotransferase) and glutamic pyruvic transaminase (alanine aminotransferase), total proteins, albumin, globulin and albumin/globulin ratio. Total bilirubin from 0.00 to 1.6 mg/dL, direct bilirubin from 0.0 to 0.4 mg/dL and indirect bilirubin from 0.0 to 1.2 mg/dL. They may range up to 15 % the enzyme's upper limit. Lower limit has no restriction for subjects' inclusion.
11. Electrocardiogram (12 leads) without clinically significant pathological signs, particular in QTc interval Bazett (normal value < 450 ms).

12. All women of childbearing potential should test negative for pregnancy qualitative and quantitative test during screening period and at the start of each visit (day -1 for each treatment period.)
13. Vital signs (blood pressure and pulse) in supine position within normal ranges or with clinically significant abnormalities as per the Principal Investigator's judgment.
  - f. Heart rate between 50 and 100 beats per minute.
  - g. Respiratory rate between 12 and 20 per minute.
  - h. Systolic blood pressure between 80 and 129 mmHg.
  - i. Diastolic blood pressure between 50 and 89 mmHg.
  - j. Forehead temperature between 36.0 and 37.0 °C.
14. All women of childbearing potential who are not pregnant or breastfeeding and who are using a highly effective contraceptive method (defined as those, alone or combined, which failure rate is low; i.e., less than 1 % a year, when used continuously and correctly) for at least one month before and following dosing. Barrier methods and intrauterine device are considered standard contraceptive methods. Hormonal methods will not be included. Post-menopausal women can be included (i.e., those with at least 12 consecutive months of amenorrhea following their last menstruation period) or surgically sterile/hysterectomy for at least 6 months before their participation in the study.
15. Negative result for alcohol breath test and urine test for drugs of abuse (opioids, barbiturates, cocaine and its metabolites, amphetamines, metamphetamines, morphine, cannabinoids, benzodiazepines and tricyclic antidepressants), at screening and at each day -1 of the 2 treatment periods.
16. Negative serology tests for human immunodeficiency virus (HIV1 and HIV2 antibodies), hepatitis A (HAV), hepatitis B (HBV), hepatitis C (HCV) and VDRL test screening.

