### **6.3.3 Study withdrawal criteria**

Subjects can be withdrawn from the study, as per the Principal Investigator's judgment, for the following reasons:

1. In case continuous participation in the trial is detrimental for subject's health, as per Investigator's judgment.
2. Hypertension signs and symptoms which require pharmacological treatment.
3. Syncope or shock.
4. Severe adverse reaction.
5. Serious Adverse Event.

6. Concurrent diseases or concomitant treatments not allowed by the protocol.
7. Lack of discipline.
8. Lack of compliance with the diet.
9. Loss of two samples within absorption period or near to the  $C_{max}$ .
10. Should emesis occur within the established time for  $t_{max}$ .
11. Data from subjects who experience emesis during the course of the bioavailability study should be removed from the statistical analysis if vomiting occurs in or after twice the median value for  $t_{max}$ .
12. If any of the participant subject, during wash-out period, takes alcoholic beverages, smokes tobacco, has xanthines containing beverages or food (coffee, tea, cacao, chocolate, mate, coke drinks, etc.) grapefruit, grapes or citrus, or grilled food (charcoal) within 24 h prior to the recruitment in the admission phase, or using any drug known by affecting the study.
13. Positive test for drugs of abuse (drug screening) such as: amphetamines, benzodiazepines, cocaine, metamphetamines, morphine and tetrahydrocannabinoids.
14. Positive pregnancy test, qualitative and quantitative test during screening period and at the start of each visit (day -1 for each treatment period) following the study drug dosing.
15. All cases where the Principal Investigator judges as lack of compliance to the protocol or which may risk final results.
16. Lost to follow-up.
17. Participation in another investigational study.
18. Any event which in the opinion of the Investigator might risk subject's safety unacceptably.

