### 8.2.1 First Administration Period

- Admission the day prior to the visit for assuring 10.5-h fasting period.
- Dinner at least 10.5 h before the dosing in fasted condition or breakfast in fed condition.
- Subject's eligibility will be checked again before catheter insertion and drug's dosing.
- Catheter insertion at the moment of blood sampling for gonadotropins determination (elective, only for women).

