#### 8.5.4      **Vital signs, ECGs, Physical Examinations and other Assessments**

At Screening, EOT and prior to each dosing, blood pressure, pulse, respiratory rate and forehead temperature (subjects should be in rest and in supine position at least 10 minutes before vital signs measurement; and they should be in rest and in supine position during the vital signs measurements) will be measured.

These values should be within the normal range (SBP between 80 and 129 mmHg and DBP between 50 and 89 mmHg) in order the subject is allowed to keep on participating in the study. Same measurements will be made during all shifts following dosing at each one of the visits. Vital signs will be measured during the 2 cross over periods as shown in the following:

- **Record of Vital Signs**

First Visit	Second Visit
Admission	Admission
Pre-dose	Pre-dose
Morning (4 hours post-dose approximately)	Morning (4 hours post-dose approximately)
Evening (8 hours post-dose approximately)	Evening (8 hours post-dose approximately)
Night (12 hours post-dose approximately)	Night (12 hours post-dose approximately)
24 and 32 hours post-dose approximately	24 and 32 hours post-dose approximately
Discharge (48 hours post-dose approximately)	Discharge (48 hours post-dose approximately)
Ambulatory samples (72, 96, 120, 144 and 168 hours post-dose approximately)	Ambulatory samples (72, 96, 120, 144 and 168 hours (EOT) post-dose approximately)

In the event any subject has clinically significant changes out of normal ranges for blood pressure and pulse during confinement post-dose, he/she will be closely observed by the medical staff. Supportive measures, as appropriate, will be taken according to the current subject's condition until they are resolved. If change persists, continuation in the study will be considered by the Principal Investigator.

At Screening, EOT and prior to each dosing and 48 hours after each IMP administration, electrocardiograms will be measured.

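### Inclusion criterion 13 on vital signs is inverted and conflicts with its own numeric limits, with items 8 and 11, and with section 8.5.4; the practical risk is low

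*Protocol*

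**What the plan says.** Protocol section 6.3.1, item 13, sets the vital-signs condition for entry. Blood pressure and pulse, taken supine, are to be "within normal ranges or with clinically significant abnormalities as per the Principal Investigator's judgment". The Summary (section 1) prints the same sentence. In both places five limits follow: heart rate 50 to 100 per minute, respiratory rate 12 to 20 per minute, systolic pressure 80 to 129 mmHg, diastolic pressure 50 to 89 mmHg, and forehead temperature 36.0 to 37.0 °C.

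Two neighbouring criteria in section 6.3.1 deal with the same kind of finding:
- Item 8, laboratory results: "within normal ranges or without clinically significant deviations as per Principal Investigator's judgment".
- Item 11: "Electrocardiogram (12 leads) without clinically significant pathological signs".

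Section 8.5.4 has blood pressure, pulse, respiratory rate and forehead temperature measured at screening, at the end of the trial and before each dose. As a condition for continuing, it says: "These values should be within the normal range (SBP between 80 and 129 mmHg and DBP between 50 and 89 mmHg". It allows no exception by judgment there, and it prints numbers for blood pressure only.

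The criteria are operative. Section 6.3 states: "Only those people who meet all inclusion criteria and no exclusion criteria will be recruited as study subjects". Section 8.2.1 adds: "Subject's eligibility will be checked again before catheter insertion and drug's dosing".

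**The concern.** The lead sentence of item 13 offers two ways to qualify: normal values, or abnormal values that the investigator considers clinically significant. The second is the opposite of what a trial in healthy volunteers needs. It turns a safety screen into something that, on its face, lets in the people it should keep out.

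Elsewhere the protocol treats such findings as warnings. After dosing, section 8.5.4 provides for a subject with "clinically significant changes out of normal ranges for blood pressure and pulse during confinement post-dose, he/she will be closely observed by the medical staff". Section 6.3.3 gives as a reason for withdrawal: "Hypertension signs and symptoms which require pharmacological treatment". A finding that calls for close observation or withdrawal after dosing cannot sensibly be a route to entry before it.

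What is at stake is the soundness of one eligibility rule that screening staff must apply. No estimate or confidence interval depends on it.

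**Working it through.** No arithmetic applies, and the plan gives no figure to reproduce. The check is a comparison of texts and of the logic they imply.

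**Step 1: is the wording isolated?** No. The same sentence stands in section 1 and in section 6.3.1, so a correction in one place would leave the other wrong.

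**Step 2: what was meant?** Item 8 has almost the same construction as item 13 but says *without*. Item 11 also says *without*. The intended sense of item 13 is therefore clear.

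**Step 3: do the listed limits rescue the sentence?** The protocol does not say whether the five limits are separate requirements or only spell out the normal ranges. Both readings have to be tried:
- Reading A, the limits define the normal ranges: item 13 is met if the value is in range OR clinically significant.
- Reading B, the limits are binding: item 13 is met if the value is in range AND (in range OR clinically significant), which reduces to in range.

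**Step 4: set both readings against section 8.5.4** (in range only) and against two possible corrections.

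| Reading of the vital sign | Item 13, reading A | Item 13, reading B | Section 8.5.4 | *Without*, limits not binding | *Without*, limits binding |
|---|---|---|---|---|---|
| In range, not significant | accept | accept | accept | accept | accept |
| In range, judged significant | accept | accept | accept | accept | accept |
| Out of range, not significant | reject | reject | reject | accept | reject |
| Out of range, significant | accept | reject | reject | reject | reject |

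These are logical cases, not frequencies.

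**Step 5: read the table.** Under reading A the literal text turns away the harmless out-of-range value and admits the significant one, and so disagrees with section 8.5.4 in the last row. Under reading B the results agree with section 8.5.4, but only because the second half of the sentence never changes an outcome and contradicts the limits below it. Neither reading leaves the sentence correct.

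**Step 6: is one word enough?** Changing *with* to *without* alone gives the fifth column. That corrects the last row but would let judgment override the limits in the third row, where section 8.5.4 rejects. Stating that the limits bind gives the last column, which matches section 8.5.4 in all four rows. A value in range but still judged significant passes both rules; item 7, on good health, is the criterion for that case.

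**The case against.** The strongest reply is that this is a slip of drafting or translation that nobody would act on, and that the gap is closed elsewhere. Section 8.5.4 requires in-range values at screening and before each dose and repeats the blood pressure limits of item 13. Item 7 requires good health. Section 6.3.3, items 1 and 18, lets the investigator withdraw anyone for whom participation is unsafe. Nearly all of this stands, and it is why the point is minor. The cover is less explicit for pulse: section 8.5.4 prints no pulse limits, so the reader must take them from item 13, the faulty item.

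Three stronger readings are tempting, and the documents do not support them.
- A reader might infer that item 13 plainly accepts a pressure such as 150/95 mmHg. That holds only under reading A. If the limits bind, 150 exceeds 129 and 95 exceeds 89, and the reading fails item 13 on its own terms.
- A reader might infer that such a volunteer would be recorded as eligible and dosed. The protocol does not show how individual criteria are recorded in the case report form, and section 8.5.4 bars that blood pressure in any case.
- A reader might want section 8.5.4 rewritten so that all five limits become an explicit stop before each dose. The error in item 13 does not require this. It could remove an already-dosed subject before period 2 for a harmless temperature or respiratory rate. Section 6.5 does not replace dropouts, and section 9.1 counts on 18 evaluable subjects of 22.

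**Conclusion.** The concern holds as a wording error with low practical risk. Item 13 is inverted in both places where it is printed, and it is inconsistent with its own limits, with items 8 and 11, and with section 8.5.4. That conclusion does not depend on how the listed limits are read. Whether the literal text actually admits a clinically significant out-of-range value does depend on it: yes under reading A, no under reading B.

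Severity is minor. The documents give no basis for estimating how many volunteers could be touched, and section 8.5.4 makes dosing such a person unlikely. The primary pharmacokinetic parameters, the sample size and the mixed-model analysis are unaffected. The one assumption about intent is that items 8 and 11 show what item 13 was meant to say.

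**What to change.** In item 13, in both section 1 and section 6.3.1:
1. Change *with* to *without* in the lead sentence.
2. Add one sentence, for example: *The numeric limits listed under this criterion are binding at screening and cannot be set aside by the investigator's judgment.*

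The pre-dose rule in section 8.5.4 stays as it is.

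The cost is an edit to one criterion printed twice. No measurement is added, since section 8.5.4 already takes all five values at screening, and nothing changes in the sample size or analysis. The downside is that a volunteer with a harmless out-of-range screening value, such as a forehead temperature of 37.1 °C against the limit of 37.0 °C, is excluded. Because the added sentence applies at screening, it does not by itself remove a subject who has already been dosed.

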### 6.3.2 Exclusion criteria:

- 1 Subjects who have received any investigational drug within 90 days prior to the study start.
- 2 Subjects who have donated or lost 450 mL or more of blood within 90 days prior to the study start.
- 3 Subjects with history of cardiovascular, renal, liver, metabolic, gastrointestinal, neurological, endocrine, or hematopoietic (any type of anemia) diseases; mental disease, surgery or other organic abnormalities which might affect the study of the investigational drug pharmacokinetics.
- 4 History of gastrointestinal tract surgery that might affect gastrointestinal absorption and/or motility as per the investigator's judgment.
- 5 Subjects with history of hypersensitivity to the study drug and/or any formulation's ingredient; history of drug induced anaphylaxis.

- 6 Subjects who take any other drug, prescribed or over the counter drugs 30 days before the study drug dose and for which at least seven elimination half-lives had not elapsed, including multi-vitamins and herbal products (e.g., St. John's Wort) including ASA and oral contraceptives for women. Except for paracetamol that can be given if required, as per the Principal Investigator's judgment.
- 7 Renal failure or renal impairment (creatinine clearance  $< 80$  mL/min), assessed by using the Cockcroft-Gault formula.
- 8 Subject's disagreement or lack of capacity to communicate and cooperate with the Investigator, lack of legal capacity or limited legal capacity which prevent him/her from continuing in the study.
- 9 Refusal of high-fat diet which is necessary to assess the food effect. Considerable deviations to the diet's normal nutritional patterns.
- 10 Subjects who have smoked tobacco, having drunk alcohol, or xanthines containing beverages or food (coffee, tea, cacao, chocolate, mate, coke drinks, etc.) above 600 mg of caffeine a day (a 240-mL cup of coffee contains 100 mg of caffeine, one cup of tea contains 30 mg and a glass of coke contains 20 mg of caffeine); those who have had grilled food (charcoal) within 24 h prior to the drug dosing (*Fuhr 1998*).
- 11 Intake of grapefruit, orange, cranberries or their juices within 14 days prior to the drug's dosing and throughout the study.
- 12 Legal inability or limited legal capacity
- 13 Incarcerated subjects.
- 14 Subjects who have been exposed to agents known as liver enzyme systems' inducers or inhibitors, or who have taken potentially toxic drugs within 30 days prior to the study.

### **6.3.3 Study withdrawal criteria**

Subjects can be withdrawn from the study, as per the Principal Investigator's judgment, for the following reasons:

1. In case continuous participation in the trial is detrimental for subject's health, as per Investigator's judgment.
2. Hypertension signs and symptoms which require pharmacological treatment.
3. Syncope or shock.
4. Severe adverse reaction.
5. Serious Adverse Event.

6. Concurrent diseases or concomitant treatments not allowed by the protocol.
7. Lack of discipline.
8. Lack of compliance with the diet.
9. Loss of two samples within absorption period or near to the  $C_{max}$ .
10. Should emesis occur within the established time for  $t_{max}$ .
11. Data from subjects who experience emesis during the course of the bioavailability study should be removed from the statistical analysis if vomiting occurs in or after twice the median value for  $t_{max}$ .
12. If any of the participant subject, during wash-out period, takes alcoholic beverages, smokes tobacco, has xanthines containing beverages or food (coffee, tea, cacao, chocolate, mate, coke drinks, etc.) grapefruit, grapes or citrus, or grilled food (charcoal) within 24 h prior to the recruitment in the admission phase, or using any drug known by affecting the study.
13. Positive test for drugs of abuse (drug screening) such as: amphetamines, benzodiazepines, cocaine, metamphetamines, morphine and tetrahydrocannabinoids.
14. Positive pregnancy test, qualitative and quantitative test during screening period and at the start of each visit (day -1 for each treatment period) following the study drug dosing.
15. All cases where the Principal Investigator judges as lack of compliance to the protocol or which may risk final results.
16. Lost to follow-up.
17. Participation in another investigational study.
18. Any event which in the opinion of the Investigator might risk subject's safety unacceptably.

